# PPD

Parameter	Calculation
Time from first insulin administration to inform consent	
Time from first insulin admin. to IC (days) = Date of IC signature - Date of first insulin admin +1.
 
Missing/partial dates will not be imputed. Anyway, since these dates are crucial for enrolment, their complete presence in the final database is expected.

Date of first/last IMP intake	
The date of first IMP intake will be taken from the Diary form (Treatment Cycle No.1, Day 1). In case of missing value, the date of dispensation of 1st kit will be used instead (CRF - IMP DISPENSATION).
 
In case of treatment discontinuation, the date of last IMP intake will be taken from the last available Diary form, otherwise the CRF date of visit reporting a Criteria for discontinuation of the IMP will be used.

Extent of exposure	
Extent of exposure (days) = Date of last IMP intake - Date of first IMP intake +1.
 
The rule for conversion from days to weeks is specified at the end of this table.

CGM parameters	See section Errore. L'origine riferimento non è stata trovata.
Identification of severe hypoglycemic event	
At Baseline: CRF - SELF REPORTED SEVERE HYPOGLYCEMIA form: Did the patient experience any severe hypoglycemic episodes?
 
At the following timepoint:
 
A subject experiences a severe hypoglycemic event if there is at least one event in SEVHYPOD form (e-diary) or SEVHYPODP form (paper diary).
 
The following rule will be applied in order to link the severe hypoglycemic event to the corresponding timepoint:
 
 
-If the date of severe hypoglycemic episodes is not missing, the event will be considered in the subsequent closes timepoint by considering the study visit and the date of severe hypoglycemic episodes
 
-If the date of severe hypoglycemic episodes is missing, it will be derived from diary data information
 

Time to severe hypoglycemic event from first dose of treatment	
Time to severe hypoglycemic event = Date of onset of severe hypoglycemic episode - Date of first IMP intake +1.
 
Date of onset of severe hypoglycemic episode will be derived according to the rule reported above.

Time from randomization to study discontinuation	Time from randomization to study discontinuation (days) = Date of study discontinuation - Date of randomization +1.
reduction in HbA1c from baseline at Time point Tx	
at Time point Tx:
 $\text{HbA1c reduction} = \text{HbA1c at } T_x - \text{HbA1c at baseline}$

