#### Secondary endpoints:

- Proportion of patients with HbA1c <7% and daily insulin requirement <0.50 IU/Kg/day [Primary endpoint. Time frame: Month 6 and 18]
- Proportion of patients with a reduction in HbA1c% > 0.5% from baseline and daily insulin requirement <0.50 IU/Kg/day [Time frame: Month 6, 12, 18]
- 2-hour AUC of C-peptide response to the MMTT [Time frame: Month 6, 12, 18]
- Time in range (TIR) by Continuous Glucose Monitoring (CGM) [Time frame: Month 6, 12, 18]
- HbA1c levels [Time frame: Month 6, 12, 18]
- Proportion of patients with HbA1c <7% who did not experience severe hypoglycemic events during treatment [Time frame: Month 6, 12, 18]  
*For the purpose of this protocol, a severe hypoglycemic event is defined as an event with one of the following symptoms: "memory loss, confusion, uncontrollable behavior, irrational behavior, unusual difficulty in awakening, suspected seizure, seizure, loss of consciousness, or visual symptoms", in which the subject was unable to treat him/herself and which was associated with either a blood glucose level <54mg/dL or prompt recovery after oral carbohydrate, i.e. glucose, or glucagon administration.*
- Additional Glucose Variability Indices derived from CGM (glucose AUC outside the target range of 70 – 180 mg/dL, 2-hour postprandial glucose (PPG), Mean Amplitude Glycemic Excursions (MAGE), continuous overall net glycemic action (CONGA)-n, Mean Of the Daily Differences (MODD), and mean daily blood glucose, SD (Standard Deviation). [Time frame: Month 6, 12, 18]
- Number of self-reported episodes of severe hypoglycemia [Time frame: Month 6, 12, 18]
- Average (previous 3 days) daily insulin requirements (IU/kg/day) [Time frame: Month 6, 12, 18]
- Estimated Glucose Disposal Rate (eGDR) [Time frame: Month 6, 12, 18]

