#### 6.4.2. Criteria for discontinuation of the IMP

The IMP will be discontinued in the case:

- QTcF is either  $> 500$  msec or increases by  $> 60$  msec from screening measurement on two consecutive ECG readings taken 1 hour apart;
- The patient develops any significant cardiovascular disease/abnormality;
- The patient develops renal (calculated eGFR  $< 60$  mL/min) or hepatic (increased ALT/AST  $> 3 \times$  ULN and increased total bilirubin  $> 3$  mg/dL [ $> 51.3 \mu\text{mol/L}$ ]) dysfunction as well as hypoalbuminemia (serum albumin  $< 3$  g/dL);
- Pregnancy occurs (female patient);
- The patient develops any significant systemic infection that must be assessed on a case-by-case basis by the investigator regarding whether they are serious enough to warrant discontinuation.
- The patient develops ketoacidosis or hypoglycemic coma.

Occurrence of any condition that qualify the patient to treatment discontinuation will be specifically monitored through ECG readings and laboratory tests obtained at the visits scheduled at the end of the 3rd (Week 11), 6th (Week 23) and 9th (Week 35) treatment cycles.

In addition, the IMP will be immediately discontinued in the event of any other possibly drug related occurrences that the Investigator believes might compromise patient's safety.

If the IMP administration is prematurely discontinued, the primary reason for discontinuation must be recorded in the eCRF. Patients who discontinue the treatment with the IMP will NOT be withdrawn from the study by default, but will be asked to complete safety and efficacy observations as per the protocol, unless otherwise they withdraw their consent.

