### 7.4.1. Additional visits during treatment

During treatment, patient will attend the center for study assessments on 2 additional visits at Month 6 (Week 26) and Month 12 (Week 52). At least 10 days before each scheduled visit, the CGM sensor will be placed.

During these visits the following will be assessed:

- Waist and waist/hip circumference and calculation of eGDR.
- Patient Diary check (information other than IMP administration at Month 6, any information at Month 12).
- Insulin requirement (IU/kg/day averaged over the previous 3 days).
- Number of self-reported episodes of severe hypoglycemia in the interval.
- Blood sampling for measurement (centralized laboratory) of HbA1c.
- MMTT. Blood samples for measurement (centralized laboratory) of C-peptide and glucose will be drawn pre-meal (2 basal samples in the range between -20 to 0) and 15, 30, 60, 90, 120 min after the meal.
- Blood sampling for measurement (centralized laboratory) of CCI [REDACTED]  
[REDACTED].
- CGM sensor download for evaluation of Glucose Variability Indices from CGM.
- Blood sampling for measurement (local laboratories) of "Safety Laboratory Tests" (Month 12 only).
- Vital signs (Month 12 only).

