**100 days (run-in phase)**

**1st insulin**

**first IMP dose**

Procedures	Screening	Baseline (within 3 weeks to C1 start)	Randomization (within 3 days of C1)	TREATMENT PERIOD (cycle = C) - 13 Cycles (C1 - C13)								FOLLOW-UP	
				C1 - C3	Week 11 (end of 3 rd cycle)	C4 - C6	Week 23 (end of 6 th cycle)	C7 - C9	Month 6 Week 26±2 Visit while on C7	Week 35 (end of 9 th cycle)	C 10 - C13	Month 12 Week 52±2	
Tests to be performed at a centralized laboratory													
Test to be performed at the local laboratory													
Informed Consent Form	X												
Eligibility criteria Randomization	X	X	X										
Auto-antibodies  & Fasting C-Peptide 	X												
Medical history	X												
BP/HR		X			X		X			X		X	X
weight, height, waist & waist/hip circumference		X							X			X	X
eGDR		X							X			X	X
Insulin requirement previous 3 days		X							X			X	X
Self Reported Severe Hypoglycemia		X							X			X	X
HLA DR-DQ haplotypes, Proinsulin,	X												
HbA1c, CCI		X							X			X	X
Safety Laboratory Test (hematology & biochemistry) 	X			X		X			X			X	X
MMTT 		X							X			X	X
Pregnancy Test	X			X		X			X			X	
12 lead ECG	X			X 		X 			X 			X 	X 
CGM download 	X 								X 			X 	X 
IMP dispensation 		X		X		X				X			
Patient Diary delivery/check		X		X		X				X		X	X
Check discontinuation criteria 				X		X				X			
Patient Phone call 			X	X	X	X	X	X	X	X	X	X	X
AE/SAE recording			X										
Prior and Concomitant Medication			X										

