### 3.6.2 Secondary efficacy endpoints

The secondary efficacy endpoints are the following:

- Proportion of patients with HbA1c <7% and daily insulin requirement <0.50 IU/Kg/day at Month 6 and 18;
- Proportion of patients with a reduction in HbA1c > 0.5% from baseline and daily insulin requirement <0.50 IU/Kg/day at Month 6, 12, and 18;
- 2-hour Area Under the Curve (AUC) of C-peptide response to the Mixed Meal Tolerance Test (MMTT) at Month 6, 12, and 18;
- Time in range (TIR) by Continuous Glucose Monitoring (CGM) at Month 6, 12, and 18;
- HbA1c levels at Month 6, 12, and 18;
- Proportion of patients with HbA1c <7% who did not experience severe hypoglycaemic events during treatment at Month 6, 12, and 18;
- Additional Glucose Variability Indices derived from CGM at Month 6, 12, and 18;
- Number of self-reported episodes of severe hypoglycaemia at Month 6, 12, and 18;
- Average (previous 3 days) daily insulin requirements (IU/kg/day) at Month 6, 12, and 18;
- Estimated Glucose Disposal Rate (eGDR) at Month 6, 12, and 18;

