## 7.2.1.6 *Proportion of patients with HbA1c <7% who did not experience severe hypoglycemic events during treatment*

Number and proportion along the 95% confidence interval (Clopper-Pearson's formula) of patients with HbA1c < 7% and absence of episodes of severe hypoglycemia during treatment will be calculated for each time point. The comparison between the two study treatment arms will be performed by means of a Chi-square test or, if more appropriate, a Fisher's Exact test at each time point.

The proportion of patients with HbA1c <7% is calculated at timepoint level: number of events occurring at a specific timepoint.

Severe hypoglycemic events are considered cumulatively and only event up to month 12 will be considered (condition will be evaluated by considering treatment period only).

In particular:

- if a subject experienced the event at a specific timepoint, it will be considered as a subject with the event for all subsequent timepoints.

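### After baseline the SAP finds severe hypoglycaemia only in diary forms and leaves out the interval count taken at the Month 6, 12 and 18 visits, so a visit-only episode is not counted

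*SAP*

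**What the plan says.** **Collection.** Protocol 7.4.1 lists, among the Month 6 and Month 12 assessments, "Number of self-reported episodes of severe hypoglycemia in the interval". Protocol 7.4.2 repeats the item for Month 18. In both sections it is a separate entry from the Patient Diary check. The SAP's own flow chart (3.2, Table 1) gives it a row, "Self Reported Severe Hypoglycemia", marked once before treatment and then at Months 6, 12 and 18. The secondary endpoint in SAP 3.6.2 is worded to match: "Number of self-reported episodes of severe hypoglycaemia at Month 6, 12, and 18".

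**Derivation.** SAP 9.1, Table 3, uses the CRF form before treatment: "At Baseline: CRF - SELF REPORTED SEVERE HYPOGLYCEMIA form: Did the patient experience any severe hypoglycemic episodes". For every later time point the rule changes to "A subject experiences a severe hypoglycemic event if there is at least one event in SEVHYPOD form (e-diary) or SEVHYPODP form (paper diary". An event with no date is dated from other diary data. The visit count is not mentioned after baseline.

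**Use.** SAP 7.2.1.6 takes the number and proportion of "patients with HbA1c < 7% and absence of episodes of severe hypoglycemia during treatment will be calculated for each time point", carries a counted event forward to all later time points and considers only events up to Month 12. SAP 7.2.1.8 fits an Andersen-Gill model to the cumulative number of events. SAP 8.1 gives Kaplan-Meier estimates of time to first severe event.

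**The concern.** The protocol collects the same outcome by two routes and the SAP reads only one. An episode that the patient tells the site about, but did not enter in the diary, does not exist for the analysis.

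The protocol's definition includes "memory loss, confusion, uncontrollable behavior, irrational behavior, unusual difficulty in awakening, suspected seizure, seizure, loss of consciousness, or visual symptoms", with the patient unable to self-treat. A missed diary entry after such an episode is plausible.

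The SAP does not treat diaries this way elsewhere:

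- For the dates of first and last IMP intake, Table 3 falls back on CRF data when the diary does not supply them.
- Average insulin requirement comes from a CRF form (SAP 7.2.1.9), although the diary also holds daily doses (Protocol 11.2).
- The other two composites have Table 3 rows that require both components to be present before a patient is a responder. The hypoglycaemia composite has no such row.

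At stake are a responder proportion that can be too high and episode counts that can be too low, when data already collected could correct both.

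**Working it through.** No figure in the plan depends on this rule, so there is none to reproduce. The check sets the sources side by side, follows a visit-only episode through each analysis, and then sizes the effect.

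**1. Sources**

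| Time point | Collected | Used to define an event |
|---|---|---|
| Baseline | CRF self-report form | CRF self-report form |
| Months 6 and 12 | Visit interval count; diary | Diary forms only |
| Month 18 | Visit interval count; diary | Diary forms only |

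**2. What happens to an episode reported at a visit but not in the diary**

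- *SAP 7.2.1.6 (composite).* The classification changes only if three conditions all hold: HbA1c is below 7% at that time point, the episode falls before Month 12, and no other diary event at that or an earlier time point already makes the patient a non-responder. An uncounted episode is not carried forward, so one missed before Month 6 can affect Months 6, 12 and 18.
- *SAP 7.2.1.8 (recurrent events).* Table 3 is the only event definition available. Each visit-only episode is one event fewer, including those between Months 12 and 18.
- *SAP 8.1 (time to first event).* The curve changes only if the missed episode was the patient's first.

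**3. Weight of one patient in the composite**

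Planned size 75 at 2:1 (Protocol 3.3): 75 × 2/3 = 50 on ladarixin and 75 × 1/3 = 25 on placebo.

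- Ladarixin: 1/50 = 2 percentage points.
- Placebo: 1/25 = 4 percentage points.

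Enrolment stopped early and the SAP does not give the final arm sizes. With n patients in an arm the weight is 100/n points, so it is larger than these figures in a smaller arm.

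**4. Illustrative overstatement of the responder proportion**

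Let h be the proportion with HbA1c below 7%, e the proportion of those with at least one severe episode, and m the share of those episode patients with no diary entry, taking the visit record as complete.

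- Diary only: h × (1 − e × (1 − m))
- Either source: h × (1 − e)
- Difference: h × e × m

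The documents give none of the three. The ranges below are assumptions: h 0.5 to 0.8, e 2% to 15%, m 10% to 50%.

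- Low end: 0.5 × 0.02 × 0.10 = 0.001, or 0.1 points.
- Example: h = 0.8, e = 0.10, m = 0.25. Diary only 0.8 × (1 − 0.075) = 74.0%; either source 0.8 × 0.90 = 72.0%; difference 2.0 points.
- High end: 0.8 × 0.15 × 0.50 = 0.060, or 6.0 points.
- If every visit-reported episode is also in the diary, m = 0 and the difference is 0.

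**The case against.** The best reply is that the visit count may not be independent. The diary asks for hypoglycaemia episodes, the investigator checks it, and its content becomes part of the eCRF (Protocol 11.2). Patients are also telephoned at least every 2 to 3 weeks (Protocol 7.1.1). The site may simply transcribe the diary at the visit. The SAP revision history shows that this derivation was updated in version 3.0, perhaps to match how the data were captured. Both sources are self-report, and confusion or memory loss also impairs recall at a visit months later. These points stand and limit the likely size. They do not close the gap, because no document says that the count is copied from the diary or that the two are reconciled.

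Stronger readings are tempting, but the documents do not support them:

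- *A blank diary is scored as event-free.* Table 3 says when an event exists and is silent on an absent diary. SAP 4.7 has a general Missing category. The case is unspecified, not explicitly coded as favourable.
- *Different sources at baseline and follow-up are themselves a fault.* The diary is first handed out at randomization (Protocol 7.2), so baseline cannot come from it.
- *A known share of events is lost, or more in one arm.* The documents give no diary capture rate and no severe-episode rate. The trial is double-blind to the last patient's Month 12 visit, and nothing suggests that diary keeping differs by arm.
- *Serious cases vanish.* Protocol 6.4.2 includes "The patient develops ketoacidosis or hypoglycemic coma" among the reasons to stop IMP, and SAP 5.3 tabulates those reasons. Such a case would be visible there, and collected data are listed (SAP 4.1), even if Table 3 did not count it.

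It is also fair that adding visit counts is not mechanical. An undated count cannot be de-duplicated by date or placed directly in the start-stop records that SAP 12.2 needs. Adding AE/SAE records as a further event source would alter an endpoint defined as self-reported.

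**Conclusion.** The point holds as a gap in the derivation. After baseline, an episode reported at a visit but missing from the diary is not counted. It produces a false responder only under the three conditions in the working. It is always lost from the recurrent-event analysis, and it affects the Kaplan-Meier curve only when it is the first event.

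The size is zero if the sources always agree. At planned size each misclassified patient is worth 2 or 4 points. The 0.1 to 6.0 point range rests wholly on assumed inputs and is not a finding of bias. The analyses are secondary or safety, and SAP 4.8 and 7 make them descriptive, so no confirmatory error rate is involved. The change is worth making because the data are already collected, but the plan does not fail without it.

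**What to change.** **Composite and episode count.** In Table 3, count a post-baseline event if it is in the diary forms or in the visit-recorded count. Where visit reports are undated, take the larger of the two counts for the interval, which is the smallest number of episodes consistent with both sources. When an interval has neither diary data nor a visit answer, set the component to missing, not to absence of an event. Add a Table 3 row for this composite, in the style of the other two.

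**Andersen-Gill and Kaplan-Meier.** Use diary dates. For visit-only events use a matching AE/SAE onset date. Where none exists, apply a stated convention, such as the interval midpoint, and show the diary-only result beside it. SAP 4.8 drops sensitivity analyses, so name this display there as an exception.

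**Reconciliation.** Use AE/SAE records for matching and dating only, and list discrepancies between diary and visit at the blind data review (SAP 4.9). If the visit count is in fact transcribed from the diary, say so in Table 3.

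**Cost.** SAP wording, a merge of data already collected, some reconciliation work, and a dating convention for visit-only events.

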## 4. Statistical Analysis

### 4.1 General

Appropriate descriptive statistics will be produced, according to the variable. For continuous data n, mean, standard deviation (SD), median and range (minimum and maximum) will be presented. For categorical data, frequency distributions and percentages will be presented.

Unless otherwise specified, hypothesis testing will be carried out at the alpha = 0.050 level (one-sided) when comparing treatments. For all inferential analyses, p-value will be rounded to three decimal places. Statistical significance will be declared if the rounded one-sided p-value will be less than or equal to 0.050.

Additional post-hoc analysis may be produced to further allow comparison between ladaxirin and placebo, according to the results obtained. Any unplanned analyses as well as deviations from the original statistical plan will be clearly documented in the Clinical Study Report.

Derivation rules for efficacy and safety analyses are reported in Table 3 in section 9.

All the data collected and derived in the study will be presented in subject data listings.

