# PPD

- no formal hypothesis testing will be performed;
- all analyses will be descriptive in nature;
- no advanced analytical methods will be applied, specifically:
  - Primary endpoint no more analyzed by means of logistic regression model: comparison between treatment arms performed by means of a Chi-square test at each time point.
  - No multiple imputation approaches to manage potential missing data;
- no sensitivity analyses will be performed;
- no sub-group analyses will be performed;

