#### *7.2.1.2 Proportion of patients with a reduction in HbA1c >0.5% from baseline and daily insulin requirement <0.50 IU/Kg/day*

Number and proportion along the 95% confidence interval (Clopper-Pearson's formula) of patients with a reduction in HbA1c > 0.5% from baseline and daily insulin requirement <0.5 (IU/kg/day) will be calculated for each time point. The comparison between the two study treatment arms will be performed by means of a Chi-square test or, if more appropriate, a Fisher's Exact test at each time point.

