## 7.2.1.5 *HbA1c levels*

HbA1c and its change from baseline will be summarized at each available timepoint and comparison between treatments will be performed by means of two-sample t-test or, if assumptions of normality are not confirmed (by Kolmogorov-Smirnov test), two-sample Mann-Whitney U test.

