# PPD

Parameter	Calculation
reduction in HbA1c > 0.5% from baseline and daily insulin requirement <0.50 IU/Kg/day at Time point Tx	at Time point T x : 

if HbA1c reduction <math>\leq 0.5\%</math> OR daily insulin requirement <math>\geq 0.50</math> IU/Kg/day, then endpoint = 'No' (even in case of one missing component)

if HbA1c reduction <math>> 0.5\%</math> AND daily insulin requirement <math><0.50</math> IU/Kg/day, then endpoint = 'Yes' (both component should be non-missing)

Conversion of Time Intervals	If a time interval was calculated in minutes, hours or days and needs to be converted into months or years the following conversion factors will be used: 

1 week = 7 days

1 month = 30.4375 days

1 year = 365.25 days

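### SAP Table 3 computes HbA1c 'reduction' with the sign reversed, so the >0.5% reduction endpoint, programmed as written, counts worsening patients as responders and true responders as failures

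*SAP*

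**What the plan says.** The protocol (Section 4.1, secondary endpoints) lists this endpoint as "Proportion of patients with a reduction in HbA1c% > 0.5% from baseline and daily insulin requirement <0.50 IU/Kg/day", at Months 6, 12 and 18. SAP Section 3.6.2 repeats it. SAP Section 7.2.1.2 plans counts, proportions, Clopper-Pearson intervals and a chi-square or Fisher test at each time point for "patients with a reduction in HbA1c > 0.5% from baseline and daily insulin requirement <0.5 (IU/kg/day".

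SAP Section 4.1 sends the programmer to one place for definitions: "Derivation rules for efficacy and safety analyses are reported in Table 3 in section 9". Two adjacent rows of Table 3 then build the endpoint:

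- The first defines the component: "HbA1c reduction} = \text{HbA1c at } T_x - \text{HbA1c at baseline".
- The second applies thresholds to that named variable. *Yes* is assigned "if HbA1c reduction > 0.5\% AND daily insulin requirement" is below 0.50 IU/kg/day. *No* is assigned "if HbA1c reduction \leq 0.5\% OR daily insulin requirement" is at or above 0.50.

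Separately, SAP Section 7.2.1.5 states that "HbA1c and its change from baseline will be summarized at each available timepoint".

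**The concern.** Tx minus baseline is the usual sign for a *change*, which is negative for an improvement. The first row calls it a *reduction*, and the second row tests it against a positive threshold. The two rows cannot both stand if the endpoint is a fall in HbA1c, which is what the protocol and the rest of the SAP describe.

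The insulin component keeps its correct direction, so the result would not be a simple mirror image of the intended endpoint. It would be a mixture of worsening HbA1c and low insulin, with no clinical meaning. Table 3 is the programming specification, so a second programmer validating against it would reproduce the same variable, and agreement between the two programs would not reveal the fault.

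**Working it through.** There is no stated figure to reproduce; the question is the sign of a derivation.

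**Algebra.** Let D = HbA1c at Tx - HbA1c at baseline, which is Table 3's *reduction*.

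- True responder: a fall of more than 0.5 points with insulin < 0.50. Then D < -0.5, hence D ≤ 0.5, so the code is *No*.
- Coded *Yes*: D > 0.5, which is a rise of more than 0.5 points, with insulin < 0.50.

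No patient can satisfy both D < -0.5 and D > 0.5, so the true responders and the patients coded *Yes* never overlap. The inversion is the same whether 0.5% is read as percentage points or as a relative change.

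**Worked cases**

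| Baseline → Tx | Insulin (IU/kg/day) | Table 3 value | Coded as written | Coded with baseline - Tx |
|---|---|---|---|---|
| 8.0 → 6.8 | < 0.50 | -1.2 | No | Yes |
| 6.5 → 7.2 | < 0.50 | +0.7 | Yes | No |
| 6.5 → 6.9 | < 0.50 | +0.4 | No | No |
| 6.5 → 7.2 | 0.60 | +0.7 | No | No |

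**Exhaustive check of the logic.** The grid takes baseline 6.0-11.0% (51 values), Tx 5.0-11.0% (61 values) and insulin 0.20-0.80 in steps of 0.05 (13 values): 51 × 61 × 13 = 40,443 combinations. Of these, 9,180 are true responders and all are coded *No*. As written, 6,210 are coded *Yes*, all of them among the 16,575 combinations with any rise in HbA1c. The overlap is 0. These counts depend on the ranges chosen and estimate nothing about the trial.

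**Effect on the between-arm comparison (illustration only).** The documents give no means, SDs or insulin proportions for this endpoint, so these are assumed. Take HbA1c change as Normal(μ, SD), independent of insulin. Then:

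- intended rate = P(change < -0.5) × P(insulin < 0.50)
- rate as written = P(change > +0.5) × P(insulin < 0.50)

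(a) HbA1c effect only: μ = -1.0 (ladarixin) vs -0.5 (placebo); 60% with insulin < 0.50 in both arms.

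| SD | Intended, ladarixin vs placebo | As written, ladarixin vs placebo |
|---|---|---|
| 1.0 | 41.5% vs 30.0% | 4.0% vs 9.5% |
| 1.2 | 39.7% vs 30.0% | 6.3% vs 12.1% |
| 1.5 | 37.8% vs 30.0% | 9.5% vs 15.1% |

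The intended difference is +7.8 to +11.5 points; as written it is -5.5 to -5.8. It reverses.

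(b) Insulin effect only: μ = -0.5 in both arms; 75% vs 55% with insulin < 0.50.

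| SD | Intended, ladarixin vs placebo | As written, ladarixin vs placebo |
|---|---|---|
| 1.0 | 37.5% vs 27.5% | 11.9% vs 8.7% |
| 1.2 | 37.5% vs 27.5% | 15.2% vs 11.1% |
| 1.5 | 37.5% vs 27.5% | 18.9% vs 13.9% |

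The intended difference is +10.0 points; as written it is +3.2 to +5.0. It does not reverse, but its size is wrong.

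**The case against.** The intent is not in doubt: the protocol, the SAP endpoint list, SAP Section 7.2.1.2 and both Table 3 row labels all say reduction. The natural reading is a slip in one formula, and a competent programmer may correct it without comment. The program for this endpoint and the mock shells (SAP Section 12.3) are not in the documents supplied, so whether the error reached any output is unknown. It would also be easy to spot: SAP Section 4.1 requires listings of all collected and derived data, and HbA1c change is reported separately, so a patient at 8.0% then 6.8% with low insulin and coded *No* would look odd.

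The stakes are limited too. This is one of ten secondary endpoints in a prematurely closed study for which SAP Section 4.8 says "all analyses will be descriptive in nature". It is not among the results to be graphed under SAP Section 7.2. The between-arm scenarios rest on assumed inputs, and the protocol's account of the previous phase 2 trial (Section 2.4.2) found no clinically relevant difference in overall insulin requirement, which lends no support to scenario (b).

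All of this limits the consequence and none of it corrects the text. Nothing in either document applies an absolute value, a sign reversal or a threshold of -0.5. A silent correction would itself depart from the SAP, whose Section 1 requires deviations to be explained in the study report. Descriptive status does not help, because the proportions and tests are still to be reported.

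**Conclusion.** The concern holds. The rule is wrong as written, and the proof needs only the two adjacent rows of Table 3. Followed literally, it codes all true responders *No* and assigns *Yes* only to rises of more than 0.5 points with insulin below 0.50. That invalidates the proportions, intervals and tests for this endpoint at Months 6, 12 and 18.

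The conclusion is conditional on the code following Table 3. The possible reversal between arms is an illustration under assumed values, not a prediction. The primary endpoint uses HbA1c < 7% and is unaffected, as is the separate summary of HbA1c change. It should be fixed because a stated derivation rule contradicts the endpoint it serves and the repair is trivial.

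**What to change.** In SAP Table 3, replace the formula with: HbA1c reduction = HbA1c at baseline - HbA1c at Tx. Leave the > 0.5% and ≤ 0.5% rules as they are.

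Add a row for HbA1c change from baseline = HbA1c at Tx - HbA1c at baseline, named separately, so that the edit cannot flip the sign of the analysis in SAP Section 7.2.1.5. This row is a safeguard; that analysis does not refer to the *reduction* variable.

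Check the analysis-dataset code against the corrected sign, using a case such as 8.0% to 6.8% with insulin below 0.50, which must return *Yes*. If outputs already exist, confirm which sign they used and document it in the study report.

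Cost: one line of SAP wording, one added table row and a one-line code check. No new data are needed.
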